**ABBREVIATIONS AND DEFINITIONS**

Abbreviation	Definition
6MWT	Six Minute Walk Test
6MWD	Six Minute Walk Distance
AE	Adverse event
AO	Ambulatory oxygen
ATS	American Thoracic Society
COPD	Chronic obstructive pulmonary disease
EC	Ethics committee
EDC	Electronic data capture
ERS	European Respiratory Society
FDA	U.S. Food and Drug Administration
FiO2	Fraction of inspired oxygen
GCP	Good Clinical Practice
GP	General practitioner
ICH	International Conference on Harmonisation
IEC	Independent ethics committee
IRB	Institutional Review Board
LTOT	Long-term oxygen therapy
LO	Liquid oxygen
mBORG	Modified BORG Scale
OC	Oxygen concentrators
POC	Portable oxygen concentrator
PPG	Photoplethysmography
SAE	Serious adverse event
SpO2	Oxygen saturation
TMF	Trial Master File

## 1. Summary

- Design:** Prospective randomized study with a cross-over design.
- Device:** All participants entered into the study will be randomized to complete a 6MWT with either of the following devices, in a cross-over fashion and with a one-hour wash-out period between tests:
- Control device (portable oxygen cylinder) first; or
  - Study device (Mobi™, POC) first.
- Objectives:** The primary objective of this study is to compare mean oxygen saturations (SpO2) between using the Mobi™ and an oxygen cylinder during the Six Minute Walk Tests (6MWTs).
- The secondary objective of this study is to evaluate the participant experience when using Mobi™ and an oxygen cylinder whilst walking, based on levels of dyspnea and distance covered during the 6MWTs.
- Primary Endpoint:** Mean SpO2 during Six Minute Walk Tests (6MWTs) for use of Mobi™ compared use of oxygen cylinder.
- Secondary Endpoints:**
- Distance covered during the 6MWTs
  - Post-6MWT SpO2
  - Time spent ≥ 90% SpO2 during 6MWT
  - Participant acceptance questionnaire around ease of use and other aspects specific to portable oxygen use
  - Dyspnea and fatigue levels measured by Modified Borg scale (mBorg)
- Enrollment:** Up to 32 participants who meet the inclusion and exclusion criteria are anticipated to be randomized for this study
- Study Site(s)** 1 site in the United States

**Selection Criteria:**Inclusion Criteria

Participants must meet all of the following inclusion criteria to be eligible for participation in this study:

1. Informed consent obtained before any study-related activities. Study-related activities are any procedures that are carried out as part of the study, including activities to determine suitability for the study.
2. Male or female, age  $\geq 18$  years at the time of signing informed consent.
3. Diagnosed with COPD and currently in a stable state (at least 4 weeks since last exacerbation episode).
4. Current prescription for long-term oxygen therapy.
5. Participant meets the criteria for pulse-dose portable oxygen delivery, defined as being mobile within the home and the qualifying blood gas study was performed at rest/ awake or during exercise.
6. Participant can read and comprehend English.

Exclusion Criteria

Participants who meet any of the following exclusion criteria are not to be enrolled in this study:

1. Clinically unstable, which in the investigator's opinion, may jeopardize the participant's safety or compliance with the protocol.
2. Current oxygen therapy prescription which requires  $>5$  L/min continuous flow.
3. Known or suspected contraindication for pulse-dose (e.g. using oxygen for life-sustaining or life-supporting purpose).
4. Unable to complete 6MWTs, e.g., unstable angina and myocardial infarction during the previous month.
5. Female who is pregnant, breast-feeding, or intends to become pregnant, or is of child-bearing potential and not using an adequate contraceptive method (adequate contraceptive measure as required by local regulation or practice).

**Duration of study:**

Participation can last up to a week, which includes a 1-hour Screening Visit, an optional 7-day screening period, and a 2.5-hour Visit 1. Screening Visit and Visit 1 may take place at the same day depending on the preference of participants, however, Visit 1 must be conducted entirely within one visit.

**2. Introduction**

The study will be conducted in compliance with this protocol, International Conference on Harmonisation Good Clinical Practice (ICH-GCP) and applicable regulatory requirements (Section 11.1.1). In this document, the term investigator refers to the individual responsible for the overall conduct of the clinical study at a study site.

## 2.1 Background

### 2.1.1 Chronic Obstructive Pulmonary Disease

Chronic Obstructive Pulmonary Disease (COPD) is characterized by progressive airflow blockage and breathing-related problems. COPD was the third leading cause of death in the United States in 2014 and is projected to be the fourth leading cause of death worldwide and seventh in morbidity burden by 2030^1-3. Smoking is by far the greatest risk factor for COPD. Other risk factors include exposure to air pollution, genetics, airway hyper-responsiveness, and poor lung growth during childhood. COPD severity can be stratified with the use of spirometry, which is a series of tests to measure the volume of air a patient can inhale, the volume of air a patient can exhale, and how quickly a patient can exhale. COPD treatment options depend directly on the severity of a patient's condition. Therapy options for COPD symptoms include: smoking cessation, pharmacologic therapy, coaching on inhaler technique, vaccinations against respiratory diseases, and pulmonary rehabilitation.

### 2.1.2 Long-term oxygen therapy

Long-term oxygen therapy (LTOT) is prescribed for patients whose COPD is considered severe. LTOT is defined by the British Thoracic Society as  $\geq 15$  hours of oxygen use per day. Oxygen is provided continuously to the patient in either a continuous-flow or pulsed delivery pattern. Patients with more significant COPD symptoms are expected to benefit from LTOT as it has been shown to improve survival, exercise, sleep, and cognitive performance. LTOT systems include oxygen concentrators (OC), liquid oxygen (LO) and portable oxygen concentrators (POCs). OCs remain the most economical way to provide oxygen at home. Many modern LTOT users are considered highly active and ambulatory when compared to their historic counterparts, who often were considered truly homebound. However, to comply with physician prescription to breathe oxygen for  $\geq 15$  hours per day, patients using many of the LTOT modalities are forced to stay at home and to limit their outdoor activities.

#### 2.1.2.1 Oxygen Cylinders – Liquid or Gas

Oxygen is delivered to the patient either via a flow meter attached to the cylinder or via an oxygen conservation device. Unlike continuous flow devices, oxygen conservation devices deliver oxygen predominantly during inspiration and therefore avoid wastage caused by oxygen flow during expiration. The most common oxygen conservation devices are 'demand flow', which deliver a pre-set volume or bolus of oxygen in early inspiration. Another type of oxygen conservation device consists of a nasal cannula set with an integrated pendant-shaped reservoir that fills with oxygen during exhalation and delivers a bolus of oxygen during subsequent inspiration. A less efficient combination is the use of an OC at home and pressurized oxygen in small lightweight cylinder for ambulation. Need for frequent refilling and cumbersome logistics make this source less convenient, for this reason, POCs represent a higher level of convenience as compared to other ambulatory systems (e.g., LO).

#### 2.1.2.2 Portable Oxygen Concentrators

Like stationary OCs, POCs separate nitrogen from ambient air and are capable of delivering 93–95% oxygen at a rate of 3–4 L/min. They are small and lightweight (maximum weight 4 kg for intermittent flow systems, or 9 kg for continuous flow systems) and can be powered by electricity, car, or rechargeable batteries. Two types of POCs are available: continuous flow and pulse flow. Unlike continuous flow oxygen, pulse flow devices provide a pre-set oxygen bolus (measured in milliliters per breath) during the first 60% of inspiration thus reducing oxygen waste. The pulse flow system is capable of delivering the same volume of oxygen per breath, regardless of respiratory rate.

POCs, such as Mobi™, have been shown to help improve moderate to severe COPD patient's functional ability, quality of life, prevent emergency room encounters, and hospital admissions by increasing compliance with oxygen therapy. There may be some improvements in quality of life with use of POCs compared with liquid oxygen cylinders, but study results are inconsistent.

## **2.2 Rationale for the Study**

Mobi™ is a relatively new POC in the market and thus it is valuable to compare data from COPD patients using supplemental oxygen against data from Mobi™ use during ambulation. The purpose of the present study is to compare Mobi™ with a continuous flow oxygen cylinder, with mean SpO2 during a 6MWT as the primary endpoint.

## **3. Description of the Medical Devices**

### **3.1 Portable Oxygen Concentrator (POC)**

Mobi™ is indicated for patients who require supplemental oxygen, including COPD patients. It provides supplemental, high oxygen concentration to these patients. It is available via prescription only and may be used in the home, institution, and hospital settings, as well as travel environments as the Mobi™ is portable.

#### **3.1.1 Reprocessing the device**

When the device is used for multiple patients, the device should be cleaned between each participant per the Mobi™ Provider Guide. The nasal cannula and inlet air filter should be disposed of and replaced between patients.

### **3.2 Portable Oxygen Cylinder**

Participant will use a portable, continuous flow E oxygen cylinder provided by the study site as a comparison.

### **3.3 Other Medical Devices**

#### **3.3.1 SpO2 Monitoring**

Pulse oximeter oxygen saturation (SpO2) and pulse rate are monitored continuously with approved devices.

##### **3.3.1.1 Oximeter**

The PalmSat 2500 oximeter (Nonin Medical, Inc) will be used in this study. Trained study staff will place the oximeter on the patient's non-dominant forefinger just before beginning each 6MWT. This study staff representative will hold the oximeter device during the 6MWT, so they can continuously monitor the SpO2 levels of the patient during this assessment.

## **4. Objectives and endpoints**

### **4.1 Objectives**

#### **4.1.1 Primary objective**

To compare mean oxygen saturations (SpO2) between using the Mobi™ and an oxygen cylinder during the Six Minute Walk Tests (6MWTs).

#### 4.1.2 Secondary objective

To evaluate participant experience when using Mobi™ and an oxygen cylinder whilst walking, levels of dyspnea and distance covered during the 6MWTs.

### 4.2 Endpoint

#### 4.2.1 Primary endpoint

Mean SpO2 during Six Minute Walk Tests (6MWTs) for use of Mobi™ compared use of oxygen cylinder.

#### 4.2.2 Secondary endpoints

- Distance covered during the 6MWTs.
- Post-6MWT SpO2
- Time spent  $\geq$  90% SpO2 during 6MWT
- Participant acceptance questionnaire around ease of use and other aspects specific to portable oxygen use
- Dyspnea and fatigue levels measured by Modified Borg scale (mBorg)

## 5. Study Design

### 5.1 Study Design

This is a prospective, randomized, cross-over study design with participants serving as their own controls. Eligible participants will complete two 6MWTs: one while using portable oxygen cylinder and one while using Mobi™. All participants entered into the study will be randomized to complete a 6MWT with either of the following devices in a cross-over fashion, with a one-hour wash-out period between tests:

- Control device (portable oxygen cylinder) first; or
- Study device (Mobi™, POC) first.

### 5.2 Study Site(s)

One (1) site in the United States will be approved to enroll participants in this study. Minimum criteria for study site qualification will be documented in the site qualification questionnaire, and filed in the Trial Master Files. Sites that initially meet the minimum criteria may be visited by a qualified monitor to further discuss study details, requirements, and expectations, as well as to ascertain adequacy of site facilities. Qualified site will be provided with the study documents necessary for IRB submission. Site readiness will be determined prior to enrollment of the first participant at the study site, and is contingent upon the electronic filing of final IRB approval letter and all other critical study documents.

### 5.3 Participant recruitment

The participants will be recruited by qualified study staff at the study site via flyer and/or telephone contact. Participants who may be interested in taking part will be told about the study details, and qualified study staff will go through the Informed Consent Form process with them. Participants are encouraged to ask questions and/or consult with family members with any questions on the study. Participant's that sign the Informed Consent Form may enroll into this study.

## 6. Study Population

Eligible COPD participants using home oxygen will be included in this study and the dropout rate is anticipated to be 5%.

### 6.1 Number of Study Participants

Number of participants planned to be screened: up to 100

Number of participants planned to be randomized: 32

### 6.2 Inclusion Criteria

Participants must meet all of the following inclusion criteria to be eligible for participation in this study:

1. Participant has given informed consent before any study-related activities. Study-related activities are any procedures that are carried out as part of the study, including activities to determine suitability for the study.
2. Participant is male or female, age  $\geq 18$  years, at the time of signing informed consent.
3. Participant has been diagnosed with COPD and is currently in a stable state (at least 4 weeks since the last exacerbation episode).
4. Participant is currently prescribed long-term oxygen therapy.
5. Participant meets the criteria for pulse-dose portable oxygen delivery. Criteria is defined as being mobile within the home and has undergone a qualifying blood gas study at rest (awake) or during exercise.
6. Participant can read and comprehend English.

### 6.3 Exclusion Criteria

Participants who meet any of the following exclusion criteria are not to be enrolled in this study:

1. In the investigator's opinion, participant is clinically unstable and their participation may jeopardize the participant's safety or compliance with the protocol.
2. Participant is currently prescribed long-term oxygen therapy of  $>5$  L/min continuous flow.
3. Participant has a known or suspected contraindication for pulse-dose oxygen (e.g. using the device for life-sustaining or life-supporting purposes).
4. Participant is unavailable to complete 6MWTs (e.g., unstable angina and myocardial infarction during the previous month).
5. Participant is a female who is pregnant, breast-feeding, or intends to become pregnant, or is of child-bearing potential and not using an adequate contraceptive method (adequate contraceptive measure as required by local regulation or practice).

## 7. Study Procedures

Participation includes a 1-hour Screening Visit, up to 7-days screening period (optional), and a 2.5-hours Visit 1. Screening Visit and Visit 1 may be combined depending on the preference of participants. Each participant is to attend both visits at the site. The Investigators must document any deviation from study procedures and notify ResMed.

### 7.1 Screening Visit

7.1.1 Participants will be screened to determine eligibility for participation in the study. Before any study-related activity, the Investigator or designee must provide the subject with the Informed Consent Form, explaining the trial and the procedures involved. Each potential

participant must sign and date the Informed Consent Form before any study-related activities are performed. Once a person agrees to participate in this trial, by signing and dating the Informed Consent Form, the following will be performed and documented at screening:

#### 7.1.2 Demography

Demography will be recorded in the eCRF at screening and consists of:

- Date of birth
- Sex
- Ethnicity
- Race

#### 7.1.3 Body weight and height

Body weight (with an empty bladder, without shoes and only wearing light clothing) must be measured and recorded in the eCRF in kilogram or pound (kg or lb), to one decimal place. The body weight should be assessed on the same scale throughout the study, if possible.

Height (without shoes) is measured in centimeters or inches (cm or in), and recorded in the eCRF to the nearest ½ cm or ¼ inch.

#### 7.1.4 COPD history and comorbidities

- Date of diagnosis of COPD
- Stage of COPD, if known
- Comorbidities
- History of Pulmonary Rehabilitation: last date of Pulmonary Rehabilitation

#### 7.1.5 Medical history

Medical history is a medical event that the participant has experienced in the past. Only relevant medical history as judged by the investigator should be reported.

The information collected for medical history includes diagnosis, date of onset and date of resolution or continuation, as applicable.

#### 7.1.6 Concomitant medication

In this study, only medications related to respiratory disease will be collected, as well as if a participant is using an antianginal medication. All relevant medications in use at time of screening through completion of the study will be recorded.

Details of any concomitant medication must be recorded at the screening visit. Changes in concomitant medication must also be recorded (for example, if participant completes Visit 1 on a different date than Screening visit).

#### 7.1.7 Oxygen prescription 

- Long-term oxygen therapy history
- POC use history
- Normal practice with oxygen use during ambulation/exertion

Participants meeting all of the inclusion criteria and none of the exclusion criteria are qualified to enroll in this study. A qualified participant can continue to Visit 1 immediately, or return to the investigational site within 7 days.

## 7.2 Visit 1

Eligible participants will be randomized into one of two study groups, which will define the order in which they use the control device or Mobi™ device during the 6MWT. The overall Visit 1 procedure is presented graphically in Figure 7-1:

[figure not shown]

Figure 7-1

The order of 6MWTs will be randomized within the EDC, and in each of the two 6MWTs the participants will use either:

- Mobi™; or
- A portable oxygen cylinder.

Site staff will pull the oxygen cylinder via a trolley or carry the Mobi™ device via its carrying bag. This will ensure consistency across tests. 6MWTs will be conducted according to current ERS/ATS field test guidelines.

### 7.2.1 Prior to 6MWT

Prior to 6MWT, the following will be performed and documented:

#### 7.2.1.1 Oxygen titration

Each participant will undergo titration using Mobi™ to reach SpO2 of  $\geq 90\%$ . After the Mobi™ titration, each participant will rest for at least 1 hour while breathing their supplemental oxygen device to obtain resting SpO2 levels. Participants shall have a resting SpO2 of  $\geq 90\%$  prior to starting each 6MWT.

During use of the oxygen cylinder 6MWT, the settings will be based on the patient's original prescription.

During the use of the Mobi™ device 6MWT, the patient will use Mobi™ based on the titrated Mobi™ setting.

After starting therapy, the site staff should also wait for approximately 5 minutes to make sure no alarms turn on. Both of these oxygen system settings will be recorded.

#### 7.2.1.2 Vital signs

- Respiratory rate
- Systolic and diastolic blood pressure should be measured in a sitting position after the participant has been resting and by using the standard clinical practice at the site.
- Pulse (beats per minute) must be recorded after the participant has been resting for 5 minutes in a sitting position.

### 7.2.1.3 Modified Borg scale

Each participant will rate their baseline dyspnea and fatigue levels using the modified Borg scale (see Appendix 4) and move to the starting point

### 7.2.2 During 6MWT

During each 6MWT, the following will be measured:

- SpO2
- Time to participant's first rest, if applicable
- Distance at point of participant's first rest, if applicable
- Number of rest times, if applicable
- 6MWD

If the participant uses walking aids (cane, walker, etc.), these aids should be used during each 6MWT.

Trained study staff will walk alongside the participant for each 6MWT. This study representative will carry the SpO2 monitor, and monitor the participant during the walk, assessing for any variables that may require the participant to rest or terminate the test (eg: study representative may terminate the 6MWT if the participant's SpO2 is below 80%).

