#### **9.1.1.3 6MWT guidelines compliance**

6MWTs will be conducted according to the guidelines (ERS/ ATS) and participants will be followed by a delegated site staff. Safety check points for immediately stopping a 6MWT in ERS/ ATS guideline will be undertaken to minimize risk associated with this test. A delegated site staff must recognize these problems and the appropriate responses. If in their clinical judgment there are signs of participant distress, the test session will be stopped and participants will be returned to their current oxygen device.

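### Staff who can see the device walk level with the participant while holding the live SpO2 display, and the visible text does not say who sets the pace; easing off when the reading falls would shrink the device difference and favour non-inferiority

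*Combined protocol and SAP*

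**What the plan says.** Section 7.2.2 fixes the attendant's position: "Trained study staff will walk alongside the participant for each 6MWT". This person carries the SpO2 monitor and must "monitor the participant during the walk, assessing for any variables that may require the participant to rest or terminate the test". Section 3.3.1.1 agrees: "This study staff representative will hold the oximeter device during the 6MWT", "so they can continuously monitor the SpO" level throughout the walk.

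Section 7.2 assigns transport of the oxygen source to staff: "Site staff will pull the oxygen cylinder via a trolley or carry the Mobi™ device via its carrying bag". The reason given there is consistency between the two tests. No section describes blinding.

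Section 9.1.1.3, on limiting risk, describes the attendant differently: "participants will be followed by a delegated site staff". For the conduct of the walk, Section 7.2 relies on an outside standard: "6MWTs will be conducted according to current ERS/ATS field test guidelines". Section 9.1.1.3 cites the same guidelines.

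Mean SpO2 during the walk is the primary endpoint (4.2.1), tested for non-inferiority with a 2-point margin (10.1). Walk distance is a secondary endpoint (4.2.2).

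**The concern.** The attendant can see the device, sees the primary-endpoint measurement as it happens, and walks where a companion can influence speed. Exertional SpO2 plausibly falls as pace rises, although the documents do not quantify this. An attendant who sees the reading fall has a natural reason to let the pace ease, and so does a participant who glimpses or hears the value. No favouritism is needed: one rule applied evenly to both devices acts more often on the device that saturates less well.

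The cross-over does not cancel such a response, because the response depends on the outcome. The analysis model in Section 10.3 has terms for treatment, period and participant only, so it cannot adjust for pace. Under the hypotheses in Section 10.1, compression of a true deficit toward zero makes a false non-inferiority finding more likely.

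**Working it through.** **1. The plan's own figure.** Inputs from Section 10.4: SDs 3.5 and 2.2, r = 0.2, true difference 0, margin 2, one-sided alpha 0.025.

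- SD of the difference = sqrt(3.5² + 2.2² − 2 × 0.2 × 3.5 × 2.2) = 3.743; the plan uses 3.74.
- SE with 30 pairs = 3.74 / sqrt(30) = 0.683.
- Non-centrality at a true difference of 0 = (0 + 2) / 0.683 = 2.93. With 28 degrees of freedom the critical t is 2.048 and the power is 80.7%. With 29 pairs the power is 79.3%.
- 30 / 0.95 = 31.6, so 32 are enrolled.

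The planned 30 evaluable and 32 enrolled are reproduced.

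**2. Direction of the effect.** Let pA and pB be the fractions of the walk, on Mobi and on the cylinder, in which pace is eased because the reading is low. Let g be the average gain in SpO2 while pace is eased. Then

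observed difference = true difference + g × (pA − pB).

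If Mobi saturates less well, pA exceeds pB and the second term is positive, so a negative difference moves toward zero. If easing is equally frequent on both devices, pA = pB and the term vanishes. Pacing that is the same in both walks and unrelated to SpO2 therefore leaves the SpO2 contrast unbiased.

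**3. Illustrative size.** The documents give neither g nor pA − pB, so the shrinkage is an assumption. The SD is held at 3.74. The false non-inferiority rate is the probability that a non-central t on 28 degrees of freedom, with non-centrality (expected observed difference + 2) / 0.683, exceeds 2.048. The true difference is −2.0 throughout.

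| Assumed shrinkage | Expected observed difference | Non-centrality | False non-inferiority |
|---|---|---|---|
| none | −2.0 | 0 | 2.5% |
| 10% | −1.8 | 0.29 | 4.7% |
| 25% | −1.5 | 0.73 | 10.5% |

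These rates belong to any bias of that size. They are not evidence that walking alongside produces one.

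**4. Are low readings plausible?** The planning study in Section 10.4 had mean walk SpO2 of 82.3% and 80.3%. Section 7.2.2 gives a reading below 80% as an example of when staff may end the test. On the plan's own inputs, staff would often be watching values near that level. The reference list shows that the study was in interstitial lung disease, so values in COPD may differ.

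**The case against.** Several objections have force.

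- **The two staff positions.** A reader might infer that 7.2.2 and 9.1.1.3 contradict each other. The verb in 9.1.1.3 stands in a paragraph about safety stops and can simply mean attended. This is wording to reconcile, and the concern does not depend on it.
- **Absence of rules.** A reader might infer that nothing governs pace or display. The documents do not support that. Sections 7.2 and 9.1.1.3 bring in ERS/ATS guidelines whose content is not reproduced. The contents list also names four appendices that are not in the text available, of which only the Borg scale is tied to one. What stands is that the visible text is silent while giving its own specific instruction on where staff walk, and site staff may well act on that instruction.
- **Matched pace.** It is tempting to say that a shared pace hides an SpO2 difference. It would tend to expose one, because a self-paced participant can slow down on the poorer device. A shared pace could compress the difference in distance, but Section 10.7 plans only estimates and confidence intervals for that endpoint.
- **Trolley and bag.** A reader might infer that the different loads set different paces. Section 7.2 has staff handle both devices for the sake of consistency, and no section says that the person holding the oximeter also moves the device. The fix below would not remove the trolley/bag difference in any case.
- **Blinding.** Hiding a cylinder trolley from the staff who handle it is scarcely feasible, so the open-label setting is context and not itself the defect.
- **View of the participant.** The attendant is also the safety observer, and walking behind could reduce the view. The wording must protect that view.

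**Conclusion.** The point holds in a limited form. Section 7.2.2 lets an attendant who can see the device, and who holds the live primary-endpoint reading, influence pace; the visible text does not restrain this. The route that matters for the primary test is easing the pace in response to a falling reading, which pulls the SpO2 difference toward zero and favours non-inferiority.

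The conclusion rests on two assumptions: that SpO2 falls with pace, and that some easing in response to the reading occurs. The documents do not show that it occurs, that participants see the display, or how large the effect would be. The rise from 2.5% to 4.7% illustrates only how sensitive the test is to a shift of 0.2 points. This is a worthwhile, inexpensive improvement to conduct; it does not show that the trial's result would be biased.

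**What to change.** Use one wording in Sections 7.2.2 and 9.1.1.3, applying to both walks:

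- Staff walk slightly behind the participant, close enough to keep the participant in view and to monitor the oximeter, and do not set the pace.
- The display is kept out of the participant's view, and SpO2 values are not spoken during the walk.
- Where possible, the same staff member attends both walks of a participant.

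Safety monitoring and stopping provisions remain as written.

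The cost is a few sentences, brief site training, and rostering one attendant for two walks that already fall within a single visit. The downside is that staff must keep a clear view of the participant from behind. The attendant will still know the device and see the reading, so the change reduces the opportunity for pacing without removing it.
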